## 4.1.3. Exclusion Criteria

Deviations from exclusion criteria are not allowed because they can potentially jeopardize the scientific integrity of the study, regulatory acceptability or patient safety. Therefore, adherence to the criteria as specified in the protocol is essential.

Patients meeting **any** of the following criteria must not be enrolled in the study:

- 1. Prior treatment with a BRAF or MEK inhibitor
- 2. Any major surgery, extensive radiotherapy, chemotherapy with delayed toxicity, biologic therapy, or immunotherapy within 21 days prior to randomisation and/or daily or weekly chemotherapy without the potential for delayed toxicity within 14 days prior to randomisation.
- 3. Taken an investigational drug within 28 days or 5 half-lives (minimum 14 days), whichever is shorter, prior to randomisation
- 4. Current use of a prohibited medication as described in Section 6.2.

- 5. Refusal of tumour and skin biopsies.
- 6. History of another malignancy.

**Exception:** Patients, who have been disease-free for 3 years, or patients with a history of completely resected non-melanoma skin cancer, and/or patients with indolent second malignancies are eligible.

- 7. Any serious and/or unstable pre-existing medical conditions (aside from malignancy exceptions specified above), psychiatric disorders, or other conditions that could interfere with the patient's safety, obtaining informed consent, or compliance with study procedures.
- 8. Known Human Immunodeficiency Virus (HIV), Hepatitis B Virus (HBV), or Hepatitis C Virus (HCV) infection (with the exception of chronic or cleared HBV and HCV infection which will be allowed).
- 9. A history of glucose-6-phosphate dehydrogenase (G6PD) deficiency.
- 10. Brain metastases are excluded unless:
  - a. All known lesions were previously treated with surgery or stereotactic surgery (whole-brain radiation is not allowed unless given after definitive treatment with surgery or stereotactic surgery), OR
  - b. Brain lesion(s), if still present, must be confirmed stable (i.e., no increase in lesion size) for ≥ 12 weeks prior to randomisation (stability must be confirmed with two consecutive magnetic resonance image (MRI) or computed tomography (CT) scans with contrast, AND
  - c. Asymptomatic with no corticosteroid requirements for  $\geq 4$  weeks prior to randomisation, AND
  - d. No enzyme inducing anticonvulsants for  $\geq 4$  weeks prior to randomisation

In addition, for patients that had brain metastases but currently have no evidence of disease (NED), NED for  $\ge 12$  weeks is required and must be confirmed by two consecutive scans, separated by  $\ge 6$  weeks, prior to randomisation.

- 11. A history or evidence of cardiovascular risk including any of the following:
  - a. LVEF < LLN
  - A QT interval corrected for heart rate using the Bazett's formula (QTcB; Appendix 3) ≥480 msec;
  - c. A history or evidence of current clinically significant uncontrolled arrhythmias;

**Exception:** Patients with atrial fibrillation controlled for > 30 days prior to randomisation are eligible.

d. A history (within 6 months prior to randomisation) of acute coronary syndromes (including myocardial infarction or unstable angina), coronary angioplasty;

- e. A history or evidence of current ≥Class II congestive heart failure as defined by the New York Heart Association (NYHA) guidelines (Appendix 4);
- f. Treatment refractory hypertension defined as a blood pressure of systolic> 140 mmHg and/or diastolic > 90 mm Hg which cannot be controlled by anti-hypertensive therapy;
- g. Patients with intra-cardiac defibrillators or permanent pacemakers;
- h. Known cardiac metastases:
- i. Abnormal cardiac valve morphology (\geq grade 2) documented by echocardiogram (patients with grade 1 abnormalities [i.e., mild regurgitation/stenosis] can be entered on study). Patients with moderate valvular thickening should not be entered on study.
- 12. A history or current evidence/risk of retinal vein occlusion (RVO) or central serous retinopathy (CSR) including:
  - a. Presence of predisposing factors to RVO or CSR (e.g., uncontrolled glaucoma or ocular hypertension, uncontrolled hypertension, uncontrolled diabetes mellitus, or a history of hyperviscosity or hypercoagulability syndromes); or
  - b. Visible retinal pathology as assessed by ophthalmic examination that is considered a risk factor for RVO or CSR such as:
    - i. Evidence of new optic disc cupping;
    - ii. Evidence of new visual field defects on automated perimetry;
    - iii. Intraocular pressure >21 mmHg as measured by tonography.
- 13. Known immediate or delayed hypersensitivity reaction or idiosyncrasy to drugs chemically related to the study treatments, their excipients, and/or dimethyl sulfoxide (DMSO).
- 14. Pregnant or lactating females
- 15. Interstitial lung disease or pneumonitis

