#### 4.1.2. Inclusion Criteria

Specific information regarding warnings, precautions, contraindications, adverse events, and other pertinent information on the GSK investigational products dabrafenib (GSK2118436) and trametinib (GSK1120212) that may impact patient eligibility is provided in the Investigator Brochures (IBs).

Deviations from inclusion criteria are not allowed because they can potentially jeopardize the scientific integrity of the study, regulatory acceptability or patient safety. Therefore, adherence to the criteria as specified in the protocol is essential.

Patients eligible for enrolment in the study must meet all of the following criteria:

- 1. Signed written informed consent;
- 2.  $\geq$ 18 years of age;
- 3. Histologically confirmed cutaneous melanoma that is either Stage IIIc (unresectable) or Stage IV (metastatic) (according to American Joint Committee on Cancer (AJCC) staging 7th edition).
- 4. BRAF V600E/K mutation-positive confirmed by a local laboratory.
- 5. Accessible melanoma tumours for biopsies (locally advanced primary melanoma or metastases)
- 6. Measurable disease according to Response Evaluation Criteria in Solid Tumours (RECIST 1.1) (Eisenhauer, 2009) on not biopsied lesions. Refer to Section 7.3.3.1 for the definition of a measureable lesion.
- 7. All prior anti-cancer treatment-related toxicities (except alopecia) must be ≤ Grade 1 according to the Common Terminology Criteria for Adverse Events version 4 (CTCAE version 4.0) at the time of randomisation.
- 8. Able to swallow and retain orally administered medication and does not have any clinically significant gastrointestinal abnormalities that may alter absorption such as malabsorption syndrome or major resection of the stomach or bowels.
- 9. Women of childbearing potential must have a negative serum pregnancy test within 14 days prior to randomisation and agree to use effective contraception, as defined in Section 7.4.3.1, throughout the treatment period, and for 4 months after the last dose of study treatment.

- 10. Eastern Cooperative Oncology Group (ECOG) Performance Status score of 0 or 1. Refer to Appendix 1 for details.
- 11. Adequate baseline organ function as defined in Table 2.

 Table 2
 Definitions for Adequate Baseline Organ Function

System	Laboratory Values
Hematologic	
ANC	$\geq 1.2 \times 10^9 / L$
Haemoglobin	≥ 9 g/dL
Platelet count	$\geq$ 75 x 10 $^{9}$ /L
PT/INR and PTT a	≤ 1.5 x ULN
Hepatic	
Albumin	≥ 2.5 g/dL

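### Exclusion 10 (brain metastases) joins its conditions as a OR b AND c AND d with no grouping, so a treated lesion that is still present can pass without being shown stable

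*Protocol*

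**What the plan says.** Protocol section 4.1.3, criterion 10, excludes patients with brain metastases unless four lettered conditions, read with their connectors, are met:

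- (a) All known lesions have had surgery or stereotactic surgery. The item ends with the limit on whole-brain radiation and the connector: "whole-brain radiation is not allowed unless given after definitive treatment with surgery or stereotactic surgery), OR".
- The next condition, (b), concerns stability and reads "Brain lesion(s), if still present, must be confirmed stable" for at least 12 weeks before randomisation, on two consecutive contrast MRI or CT scans. It ends with AND.
- (c) "Asymptomatic with no corticosteroid requirements for" at least 4 weeks. It ends with AND.
- (d) "No enzyme inducing anticonvulsants for" at least 4 weeks.

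A separate paragraph adds a rule "for patients that had brain metastases but currently have no evidence of disease (NED), NED for" at least 12 weeks, confirmed on two consecutive scans at least 6 weeks apart.

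Section 4.1.3 allows no deviation from the exclusion criteria. Section 3 bars waivers except for immediate safety concerns. Nothing in the protocol or SAP says how the OR and the ANDs are to be grouped.

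**The concern.** The OR after (a) makes prior local treatment an alternative to stability. Yet (b) speaks of any lesion still present, which naturally includes one left behind after treatment. If the connector is followed, the 12-week rule does not bind a treated patient with residual disease.

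A second gap depends on the grouping. If (c) and (d) attach only to (b), a treated patient with neurological symptoms or on corticosteroids is eligible. If they attach to both routes, that patient is not.

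Since deviations are barred, the printed connector decides who enters. At stake are the safety of patients with active brain disease and whether two careful sites would reach the same decision on the same patient.

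**Working it through.** There is no planned figure to reproduce, because the question is the logic of an eligibility rule. Let a, b, c and d be 1 when the condition is met, for a patient with a brain lesion still present.

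Two groupings keep the OR:

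- G1 (looser): a OR (b AND c AND d)
- G2: (a OR b) AND c AND d

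Two rewordings close the gap:

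- F1 (prior treatment mandatory): a AND b AND c AND d
- F2 (treated or untreated): b AND c AND d

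**Step 1: treated, residual, not shown stable, otherwise well** (a=1, b=0, c=1, d=1).

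- G1 = 1 OR (0 AND 1 AND 1) = 1
- G2 = (1 OR 0) AND 1 AND 1 = 1
- F1 = 1 AND 0 AND 1 AND 1 = 0
- F2 = 0 AND 1 AND 1 = 0

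So the missing stability requirement does not depend on which OR grouping is chosen.

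**Step 2: the other patterns, with d=1.**

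| Patient with a lesion still present | (a,b,c) | G1 | G2 | F1 | F2 |
|---|---|---|---|---|---|
| Treated, stable, (c) met | 1,1,1 | in | in | in | in |
| Treated, not shown stable, (c) met | 1,0,1 | in | in | out | out |
| Treated, stable, (c) not met | 1,1,0 | in | out | out | out |
| Treated, not shown stable, (c) not met | 1,0,0 | in | out | out | out |
| Untreated, stable, (c) met | 0,1,1 | in | in | out | in |

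The three remaining patterns (untreated, failing b or c) are refused by all four. G1 and G2 disagree exactly where a treated patient fails (c). If d is allowed to vary, they also disagree where a treated patient fails (d). These rows are logical cases, not patients.

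**Step 3: does another rule close the gap?**

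- Exclusion 2 ("Any major surgery, extensive radiotherapy, chemotherapy with delayed toxicity, biologic therapy, or immunotherapy within 21 days prior to randomisation") is a washout after treatment and does not ask whether a lesion is stable.
- Exclusion 7 ("Any serious and/or unstable pre-existing medical conditions") is a general clause with no time period.
- Inclusion 7 ("All prior anti-cancer treatment-related toxicities (except alopecia) must be" Grade 1 or lower) concerns toxicity. Inclusion 10 (ECOG 0 or 1) concerns performance status. Neither sets a stability or steroid-free period.
- Table 18 lists corticosteroids only as medications to use with caution.
- Section 7.1.2 and Table 19 require one baseline brain scan of every patient. One scan cannot show stability. The later scans in Table 19 footnote 5 come after entry.
- For (d) the gap is small. Exclusion 4, section 6.2 and Table 17 already prohibit strong inducers such as carbamazepine, phenobarbital and phenytoin for 28 days or 5 half-lives, whichever is shorter.

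**Step 4: comparison with the no-evidence-of-disease rule.** A patient with no remaining brain disease must show 12 weeks free of it on two scans. Under the OR, a treated patient with residual disease has no such wait. The literal rule is therefore stricter for the patient with less disease.

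**The case against.** The OR may be deliberate: one route for definitively treated lesions, another for lesions still present and stable. On that view (b) governs only its own route and nothing contradicts it. Conversely, a site that takes the words of (b) at face value already applies the 12-week rule to every residual lesion. Either way, the sponsor's intent, including on untreated stable lesions, cannot be established from the documents. This stands. It turns the point into a request for the sponsor to decide and state the rule, but it does not remove the need, because the text supports readings that admit different patients.

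Exclusion 7 also gives an investigator grounds to refuse an unstable or symptomatic patient, and the symptomatic or steroid-dependent case arises under only one of the two groupings. Both are fair, but a discretionary clause does not replace a stated period.

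A reader might infer three stronger things that the documents do not support:

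- *That criterion 10 contradicts the no-evidence-of-disease paragraph.* It does not. That paragraph covers patients with nothing left to see, a different group, and each patient can satisfy the rule that applies. The result is an anomaly.
- *That Arm B patients would be left on trametinib alone for 8 weeks with uncontrolled brain disease.* Section 3 lets patients who progress during monotherapy move to the combination early, and Table 19 footnote 5 calls for follow-up brain scans in patients with documented metastases at baseline and when symptoms suggest progression.
- *That the background trials size the problem.* In section 1.1.2, 273 of 322 patients were V600E-positive with no prior brain metastases. The other 322 − 273 = 49 may include V600K patients without brain metastases, and the figure says nothing about treated lesions not yet stable.

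**Conclusion.** The concern holds as an unresolved eligibility rule. Under both groupings that keep the OR, a treated patient with a residual lesion not shown stable can enter, although (b) is worded to cover any lesion still present. Under the looser grouping, a treated patient who is symptomatic or on corticosteroids can enter too. No other criterion sets a stability or steroid-free period.

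The size is qualitative. The documents do not allow a patient count or a harm rate, and none is claimed. The p-ERK endpoint, the sample size and the power are unaffected.

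The conclusion assumes that (a) to (d) form one flat list, as their consecutive letters suggest, and that sites follow the printed connectors because deviations are barred. That the OR is a slip for AND is plausible but not shown. The wording should be corrected on grounds of patient safety and consistency between sites.

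**What to change.** Reword criterion 10 so that:

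1. any brain lesion still present must be confirmed stable for at least 12 weeks on two consecutive contrast MRI or CT scans; and
2. (c) and (d) apply to every patient with brain metastases.

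Keep the no-evidence-of-disease paragraph.

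The sponsor then states whether prior local treatment is mandatory. If it is, replace the OR after (a) with AND. If it is not, write (treated or untreated) into (b) and remove (a) as a separate route, since leaving the OR in place would keep the gap open.

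**Cost.** A protocol amendment with the ethics review that section 10.2 requires, and a letter to sites. No new type of procedure is needed: a baseline brain scan is already mandatory and (b) already specifies two consecutive scans. Treated patients whose residual lesions are not yet shown stable, or who are symptomatic or on steroids, are delayed or excluded. If prior treatment becomes mandatory, untreated, stable, asymptomatic patients, who are eligible under both OR groupings, are lost as well. The (treated or untreated) wording keeps them.

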# 4.2. Permanent Discontinuation from Study Treatment and Patient Completion Criteria

# 4.2.1. Permanent Discontinuation from Study Treatment

Patients will receive study treatment when on combination therapy until disease progression, death or unacceptable adverse event, including haematologic or other non-haematologic toxicity, and/or meeting stopping criteria for liver chemistry defined in Section 5.9.1. A patient will be allowed to continue on monotherapy (either dabrafenib or trametinib) if only one study drug is permanently discontinued.

**Note:** Continuation of combination study treatment beyond radiographic or clinical disease progression (as defined by RECIST 1.1) may be possible if the investigator determines that patient has clear evidence of clinical benefit from study treatment, continuing study drugs may be in the best interest for the patient and the patient is willing to continue on study drugs. In this case, consultation between the investigator and the GSK Medical Monitor is mandatory. If continuing the patient on study treatment is agreed then all study procedures, including tumour assessments, must be followed as scheduled (Table 19). In addition, after each tumour assessment, the investigators must confirm with the GSK Medical Monitor that the patient is still benefiting from study treatment and therefore can continue receiving study treatment.

In addition study treatment may be permanently discontinued for any of the following reasons:

- deviation(s) from the protocol
- request of the patient or proxy
- investigator's discretion
- patient is lost to follow-up
- study is closed or terminated.

The primary reason study treatment was permanently discontinued must be documented in the patient's medical records and in the electronic case record form (eCRF).

If the patient voluntarily discontinues from treatment due to toxicity, 'adverse event' will be recorded as the primary reason for permanently discontinuation on the eCRF.

Once a patient has permanently discontinued from study treatment, the patient will not be allowed to be retreated

All patients who discontinue from study treatment will have safety assessments as specified in Time and Events Table (Table 19) under End-of-study visit.

# 4.2.2. Patient Completion and Withdrawal

A patient will be considered to have completed the study if the patient has disease progression or dies during the study treatment.

A patient will be considered to have withdrawn from the study if the patient has stopped study treatment due to toxicity, has withdrawn consent or if the study is

# 2012N132406\_01 **CONFIDENTIAL** BRF116613

closed/terminated. The investigator should attempt to complete the End-of-study assessments as detailed in the Times and Events Table (Table 19).

There is no survival follow-up on patients. For patients who did not progress on study drug but withdrew due to toxicity the individual's observation will be censored.

# 5. STUDY TREATMENTS

The term 'study treatment' is used throughout the protocol to describe any combination of products received by the patient as per the protocol design. Study treatment may therefore refer to the individual study treatments or the combination of those study treatments.

# 5.1. GSK Investigational Products

#### 5.1.1. Dabrafenib

Dabrafenib will be provided as 50 mg and 75 mg capsules. Each capsule will contain 50 mg or 75 mg of free base (present as the mesylate salt). Dabrafenib will be provided to sites by GSK. The contents of the label will be in accordance with all applicable regulatory requirements.

#### 5.1.2. Trametinib

Trametinib study medication will be provided as 0.5 mg and 2.0 mg tablets. Each tablet will contain 0.5 mg or 2.0 mg of trametinib parent (present as the DMSO solvate). Trametinib will be provided to sites by GSK. The contents of the label will be in accordance with all applicable regulatory requirements.

Under normal conditions of handling and administration, investigational product is not expected to pose significant safety risks to site staff. Material Safety Data Sheets (MSDS) describing the occupational hazards and recommended handling precautions will be provided to site staff if required by local laws or will otherwise be available from GSK upon request.

# 5.2. Dosage and Administration

Please refer to Section 5.8 for rules for dose modifications.

No special preparation of study medication is required.

Study treatments will be administered as follows:

- Dabrafenib, 150 mg, BID
- Trametinib, 2.0 mg, once daily

Both study treatments should be administered **in the morning** at approximately the same time every day. The second dose of dabrafenib (150 mg) should be administered approximately 12 hours after the morning dose. Study medication should be taken orally with approximately 200 mL of water under fasting conditions, either 1 hour before or 2 hours after a meal. During the combination therapy, if administration of trametinib is interrupted or permanently discontinued, administration of dabrafenib may be continued. If administration of dabrafenib is interrupted, administration of trametinib may continue.

If a patient vomits after taking study medication, the patient should be instructed not to retake the dose and should take the next dose as originally scheduled.

If a patient misses a dose, the patient may take the dose immediately if the next dose is scheduled for at least 6 hours later. If the next scheduled dose is due in less than 6 hours, the patient should skip the dose and resume dosing at the next scheduled dose.

Patients should abstain from ingestion of any food or drink containing grapefruit and grapefruit juice, Seville oranges, or pomelos within 7 days prior to randomisation until treatment discontinuation, as these have been shown to inhibit CYP3A4 activity.

Patients should start treatment as soon as possible after randomisation but no later than 72 hours post-randomisation.

# 5.3. Handling and Storage of Study Treatment

Dabrafenib, trametinib must be dispensed and administered in accordance with the protocol, and only to patients enrolled in the study. Dabrafenib and trametinib must be stored in a secure area under the appropriate physical conditions for the product. Study medication is to be stored at the temperature specified on the label. Maintenance of a temperature log (manual or automated) is required. Access to and administration of dabrafenib and trametinib will be limited to the investigator and authorized site staff.

Procedures for final disposition of unused study treatments will be provided in the SPM.

# 5.4. Treatment Assignment

Patients will be identified by a unique patient number that will remain consistent for the duration of the study.

Upon completion of all the required screening assessments, eligible patients will be registered into RAMOS (Registration and Medication Ordering System), the GSK interactive voice response system (IVRS), by the investigator or authorized site staff. RAMOS allows study sites to register and randomise patients, and also records stratification information.

Randomisation will be done centrally using a randomisation schedule generated by the GSK Biostatistical Department, which will assign patients in a 1:1:1 ratio to:

- Dabrafenib monotherapy followed by dabrafenib and trametinib combination therapy;
- Trametinib monotherapy followed by dabrafenib and trametinib combination therapy;
- Dabrafenib and trametinib combination therapy

Once a randomisation number has been assigned it must not be re-assigned even in cases of errors.

# 5.5. Blinding

This is an open-label study

# 5.6. Product Accountability

In accordance with local regulatory requirements, the investigator, designated site staff, or head of the medical institution (where applicable) must document the amount of investigational product dispensed and/or administered to study patients, the amount returned by study patients, and the amount received from and returned to GSK, when applicable. Product accountability records must be maintained throughout the course of the study. Refer to the SPM for further detailed instructions on product accountability.

